1.3 SCHEDULE OF ACTIVITIES

Study time-points and corresponding activities for ALL	Visit 1 Prenatal				Visit 2 Age 1 to 2			Visit 3 Age 2 to 3			Visit 4 Age 3+		
study participants in the experimental and control groups	Visit 1 at WIC	1-Month Follow-up	3-Month	9-Month Follow-up	Visit 2 at WIC	l -Month Follow-un	3-Month	9-Month Follow-up	Visit 3 at WIC	l -Month Follow-up	3-Month	9-Month Follow-up	Visit 4 at WIC
Informed Consent	\checkmark												
Group randomization	\checkmark												
Mother demographic questionnaire	~												
Mother knowledge questionnaire	~	✓		~	✓	~		~	✓	✓		~	✓
Mother behavior questionnaire	~	✓		~									
Intervention videotaped oral health message	~				~				✓				
Internalization questionnaire	~				~				~				
Health care climate questionnaire (HCCQ)	~				~				~				
Booster videotaped oral health message			~				✓				~		
Child plaque sample					\checkmark				\checkmark				✓
Child dental exam: plaque, caries and tooth status recordings					✓				~				✓
Child behavior questionnaire				~	✓	~		~	✓	~		~	~
Mother & child demographic questionnaire					~				~				✓
Mother behavior intent questionnaire													✓

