- Booster messages will be sent to mothers at *three-month follow-up* after viewing the videotaped oral health messages at visits 1, 2 and 3 to help them overcome the difficulties of adopting the suggested behaviors. The booster messages for mothers of Group 1 will be autonomous-supportive, while neutral for mothers of Group 2. Viewing of the 3-month booster message is optional.
- In order to assess long-term behavioral changes, all study mothers will be asked to complete again the post-intervention questionnaires at *nine-month follow-up* after viewing the videotaped messages at visits 1, 2 and 3. According to the informed consent approved by the UI IRB, "You (study participant) may feel uncomfortable in answering certain questions and you can choose to decline any aspect of the study at any time. You and your child may discontinue participating at any time without any negative consequences." Therefore, participants may choose not to complete the nine-month follow-up questionnaires.

- Each child will be examined at 12, 24 and 36 months of age (visits 2, 3 and 4) for visible plaque and dental caries by one of the examiners who will be blinded to participants' group assignment. We will utilize the d₁d₂₋₃ mfs caries criteria for scoring dental caries for the children.
- Plaque samples will also be obtained from all participating children at visits 2, 3 and 4. Numbers of MS will be derived for each sample through the standard matrix counting methodology of the spiral plating system. Plaque samples will be obtained by using sterile cotton swabs; all teeth surfaces will be swabbed. Cotton swabs will be immersed in sterile transport fluids and kept cold for transport to the microbiology labs. All laboratory procedures will be done by an experienced research scientist and under the overall guidance of [name], Professor of Microbiology & Infectious Diseases. [name] will routinely audit the database and reconcile it to a logbook that has the identification numbers for the samples stored in the ultralow freezer on a monthly basis.

Detailed Description of the Study Intervention

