9 STATISTICAL CONSIDERATIONS

9.1 STATISTICAL HYPOTHESES

- Primary Efficacy Endpoint(s):
 - Lower caries incidence
- Secondary Efficacy Endpoint(s):
 - Better knowledge, behavior towards the child's oral health, and levels of salivary MS and visible plaque scores

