9.4.3 ANALYSIS OF THE SECONDARY ENDPOINT(S)

Secondary efficacy

Secondary outcomes of interest include changes in knowledge and oral health behaviors of mothers, as well as plaque and microbial outcomes in children. Knowledge outcomes will be measured pre and post intervention via the score on the knowledge assessment. These measures will be considered as counts. GEE modeling will be used with Poisson or negative binomial distributions considered. Results will be presented as incidence rate ratios and 95% confidence intervals.

Maternal change in behavior will be assessed via a set of behavioral questions asked at multiple time points. Each individual question will be dichotomized into improved vs. did not improve based on the answers given pre and post intervention. When analyzing single time points, logistic modeling will be used. To evaluate behavioral changes over time, GEE models with a logit link function will be used. Results will be presented as odds ratios and 95% confidence intervals.

Visible plaque will be analyzed as the number of maxillary and mandibular incisors and molars with plaque at each visit. Analysis of plaque outcomes will focus on Poisson and/or negative binomial modeling, possibly with variance inflation and zero inflation accommodation, as appropriate. To account for repeated longitudinal measurements, GEE will be used to model these counts. Results will be presented as incidence rate ratios and 95% confidence intervals.

Levels of salivary MS will be reported as numbers of bacteria from each visit. Log transformation will be considered if data is skewed, and GEE models assuming a normal distribution with an identity link will be used when analyzing multiple time points. Results will be presented as adjusted least squares means estimates and 95% confidence intervals.

The same covariates as the primary endpoint will be used for both bivariate and multivariable modeling, subject to the constraint of 10 observations/events for every covariate included. Missing data may be addressed via multiple imputation. An AR(1) correlation structure will be assumed for all longitudinal models. QIC will be used for all model/covariate selection involving GEEs; AIC will be used for models calculated for single time points. Mediation analyses will proceed via Baron and Kenny's⁷⁴ steps for mediation analysis and significance will be calculated via Sobel tests.

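### Visible plaque is a raw tooth count with no allowance for teeth erupted, which costs precision mainly at 12 months, and the endpoint named salivary MS is measured only in a plaque swab.

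*Protocol*

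**What the plan says.** **Plaque.** Section 9.4.3 of the protocol defines the outcome: "Visible plaque will be analyzed as the number of maxillary and mandibular incisors and molars with plaque at each visit". The model follows: "Analysis of plaque outcomes will focus on Poisson and/or negative binomial modeling, possibly with variance inflation and zero inflation accommodation, as appropriate". Repeated visits are handled by GEE, and results are given as incidence rate ratios. No number of teeth present, proportion or offset is mentioned, and no rule covers a child with none of the scored teeth. The covariates of the primary model, which include age, carry over. The Schedule of Activities (1.3) lists "Child dental exam: plaque, caries and tooth status recordings" at Visits 2, 3 and 4. The procedures table in 6.1.2 places Visit 2 at 1 year ± 2 months.

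**MS.** Section 9.1 lists "levels of salivary MS and visible plaque scores" among the secondary endpoints, and 9.4.3 says: "Levels of salivary MS will be reported as numbers of bacteria from each visit". The synopsis (1.1) and objective 2c in section 3 also use the salivary label. On collection, 6.1.2 says: "Plaque samples will be obtained by using sterile cotton swabs; all teeth surfaces will be swabbed". It continues: "Numbers of MS will be derived for each sample through the standard matrix counting methodology of the spiral plating system". The only specimen row in the Schedule is "Child plaque sample".

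**The concern.** A count of teeth with plaque has a ceiling equal to the number of scored teeth in the mouth. Between about 10 and 14 months of age that ceiling varies from child to child. A child with 2 of 2 teeth affected scores 2, which is better than a child with 3 of 12 affected. A child with no erupted incisors or molars has a count of 0 by definition, the same as a child whose teeth are all clean. Variation in eruption therefore enters the outcome as noise, and the 12-month mean is hard to read as a measure of oral hygiene.

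The MS problem is of a different kind. The objective, the hypothesis and the analysis section all name a specimen that no procedure collects. If the label stays, the trial's report will claim a salivary effect on the evidence of plaque.

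**Working it through.** **1. The plan's own figures.** Section 9.2 sizes the trial for caries only, so there is no plan figure for plaque or MS to reproduce. Its retention assumption does reproduce: 317 × 0.79 = 250.4, 317 × 0.79² = 197.8 and 317 × 0.79³ = 156.3. That gives about 250, 198 and 156 children per arm at 12, 24 and 36 months. The stated 156 is the three-year figure.

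**2. Where the noise enters.** Let T be the number of scored teeth present, Y the number with plaque, p the plaque probability per tooth and ρ the within-child correlation. The variance of the log mean count in one arm is (A + B)/n, where

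- A = (SD of T / mean of T)², the eruption part;
- B = [(1 − p)/p] × [E(T) + ρ(E(T²) − E(T))] / E(T)², the plaque part.

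Dividing by teeth present removes A and leaves B. The fraction of variance saved is A/(A + B). Sample size cancels.

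**3. Numbers put in.** The protocol gives no eruption or plaque figures, so all of these inputs are assumptions: p from 0.3 to 0.6 and ρ from 0.2 to 0.4.

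*12 months, mean 6 teeth, SD 2.5.* A = (2.5/6)² = 0.174 and E(T²) − E(T) = 42.25 − 6 = 36.25.

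| p | ρ | B | saved |
|---|---|---|---|
| 0.3 | 0.2 | 2.333 × 13.25/36 = 0.859 | 17% |
| 0.3 | 0.4 | 2.333 × 20.5/36 = 1.329 | 12% |
| 0.6 | 0.2 | 0.667 × 13.25/36 = 0.245 | 41% |
| 0.6 | 0.4 | 0.667 × 20.5/36 = 0.380 | 31% |

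*24 months, mean 14 teeth, SD 1.8.* A = (1.8/14)² = 0.0165. B is 0.608, 1.049, 0.174 and 0.300 in the same order, so the saving is 3%, 2%, 9% and 5%.

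These figures ignore the planned age covariate. A simulation of the same settings with exam age in the model (true ratio 0.8) gave 11-27% at 12 months and between about 0 and 8% at 24 months. Age therefore absorbs part of the noise but not all of it.

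**4. Power and bias.** A second simulation, without age adjustment, assumed control plaque probability 0.30, true ratio 0.75, ρ of 0.1 or 0.3, and 250/198/156 per arm.

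| Setting | Raw count, ρ 0.1 / 0.3 | Per tooth, ρ 0.1 / 0.3 |
|---|---|---|
| 12 months, mean 6, SD 1 | 96.5% / 81.1% | 96.6% / 82.1% |
| 12 months, mean 6, SD 2 | 92.8% / 77.9% | 95.5% / 80.5% |
| 12 months, mean 6, SD 3 | 88.7% / 71.7% | 95.3% / 77.7% |
| 12 months, mean 4, SD 3 | 74.1% / 58.8% | 88.9% / 68.0% |
| 24 months, mean 14, SD 2 | 98.6% / 80.2% | 99.1% / 80.0% |

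At 36 months the two analyses agreed within 0.2 points. The raw count gave an estimated ratio of 0.748 to 0.751 in every setting, against a true 0.75. Its rejection rate under no effect was 4.1% to 6.0%. The share of children with no scored teeth was about 3% at mean 6, SD 3, and about 12% at mean 4, SD 3. It was about 2% in the settings of step 3.

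**5. Pooled over visits.** Section 9.4.3 fits one longitudinal model. Simulated pooled three-visit models gave variance savings of about 1%, 0%, 10% and −1% in four settings, and about 0-9% in a separate run.

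**6. The specimen.** No arithmetic applies. Four places use the salivary label: 1.1, objective 2c, 9.1 and 9.4.3. The Schedule, 6.1.2 and 8.1 describe plaque collection only, and 2.3.1 lists only a dental examination and plaque sampling as procedures on the child. No saliva is collected anywhere.

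**The case against.** Several points on the other side stand.

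- **No bias.** A message style is unlikely to change tooth eruption, and allocation is randomised. The simulations show no arm bias and no inflation of type I error. A reader might infer that uneven eruption distorts the arm comparison; it does not.
- **Small loss.** The loss falls on one visit of a secondary endpoint and largely disappears in the pooled model. If eruption varies by an SD of only 1 tooth, the power difference at 12 months is 1 point or less.
- **Toothless infants.** A reader might infer that they are counted as successes. The protocol defines no success and has no rule for such children. They could be recorded as not assessable, and the optional zero-inflation term could absorb some zeros.
- **MS totals.** A reader might infer that the MS number grows with the number of teeth swabbed. The protocol gives no MS unit, a log transformation may be applied, and nothing here quantifies such a dependence.
- **Legitimate choice.** Teeth with plaque per child is a valid measure of total burden. An offset changes what is estimated.
- **SAP and extraction.** An offset and a not-assessable rule can be set in a statistical analysis plan, which is not shown. The endpoint cells for objective 2c are cut off in the text available.

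What does not stand is that nothing needs changing. The protocol fixes the outcome as a count, and zero inflation does not deal with unequal ceilings among children who have teeth. The specimen contradiction lies within the protocol's own objective, hypothesis and procedures, so a later analysis plan cannot by itself remove it.

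**Conclusion.** The point holds in two limited parts.

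First, the raw plaque count gives up precision and interpretability, essentially at 12 months. The size is roughly 10-35% of the variance of the log ratio when eruption varies appreciably, and about 0 to 15 points of power in the settings tried. Little or nothing is lost at 24 and 36 months, and about 0-10% of variance in a pooled model. All of these sizes rest on assumed eruption, plaque and correlation figures that the protocol does not supply. The power figures omit the age covariate and so lean towards overstating the loss.

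Second, the salivary label contradicts the plaque-only sampling. This part needs no assumption.

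The documents do not support reading this as bias between arms, as a rule that scores toothless infants plaque-free, or as proof that MS is a total over erupted teeth. Both parts are worth correcting because the correction costs almost nothing.

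**What to change.** 1. In 9.4.3, model the number of teeth with plaque with log(number of erupted incisors and molars examined) as an offset, taken from the tooth status already recorded at each examination.
2. State that a child with no such teeth is not assessable for plaque at that visit.
3. In 1.1, 3, 9.1 and 9.4.3, replace the salivary label with MS in the pooled dental plaque swab, or otherwise reconcile these passages with the Schedule and 6.1.2.
4. State the unit of the MS result. Adjusting MS for the number of teeth swabbed is optional.

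The cost is wording and one model term, with no new data or procedures. There are two downsides. Children with no scored teeth leave the plaque model at that visit, and the estimate becomes a ratio per tooth present rather than per child. If the per-child burden is wanted, the raw count can be kept as a supporting analysis.

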9.4.4 SAFETY ANALYSES NA

9.4.5 BASELINE DESCRIPTIVE STATISTICS

Baseline descriptive analysis

For continuous demographic variables, the mean, median, and range will be calculated for each group (intervention and control). For categorical demographic variables, the frequency and percent of each category will be calculated for each group.

9.4.6 PLANNED INTERIM ANALYSES

Planned interim analysis

No interim analyses are planned.

9.4.7 SUB-GROUP ANALYSES

To determine whether the effect of the assigned intervention is consistent across subgroups, similar models for both primary and secondary endpoints will be fit and estimated including but not limited to the following:

- Mother education level
- First time mother or not
- Mother income
- Mother race
- Mother oral health status
- Mother age (< 25 vs. 25 or older)

No subgroup analysis by sex will be performed, as only pregnant individuals will be enrolled in the study.

9.4.8 TABULATION OF INDIVIDUAL PARTICIPANT DATA

Tabulation of individual participant data

Data will be de-identified and presented anonymously.

9.4.9 EXPLORATORY ANALYSES

Exploratory analysis NA

10 SUPPORTING DOCUMENTATION AND OPERATIONAL CONSIDERATIONS

10.1 REGULATORY, ETHICAL, AND STUDY OVERSIGHT CONSIDERATIONS

10.1.1 INFORMED CONSENT PROCESS

10.1.1.1 CONSENT AND OTHER INFORMATIONAL DOCUMENTS PROVIDED TO PARTICIPANTS

Prior to the beginning of the study, the PI must have IRB approval for the protocol and any informed consent forms. Any other information provided to the participants must have IRB approval. Only the PI or research team members approved by the IRB may administer consent. A person is qualified to administer consent only if he/she has received basic human subject's protection training and possesses the requisite dental and/or medical training, knowledge of the protocol and familiarity with the clinical needs to be able to discuss the risks and benefits of the study with prospective participants.

Informed consent is a process that is initiated prior to the individual agreeing to participate in the study and continues throughout study participation. Extensive discussion of risks and possible benefits of study participation will be provided to participants and their families. Consent in this study will be sought from all WIC-enrolled pregnant women interested in participating in the study. The consent of each pregnant woman will be obtained in a quiet private space by a trained research member. The consent form will be reviewed verbally. Throughout the consent process, the research member will ask the pregnant woman if she has any questions. The staff member will make sure the individual has adequate time to consider all options. If the individual appears to need more time to consider all options, staff will provide the option to participate at a later time. All pregnant women will be given the study staff's contact information in case they decide to join the study. Informed consent will be administered electronically via REDCapTM web-based research software.

The participant will be asked to sign the informed consent form electronically in REDCapTM prior to any study-related assessments or procedures. All participants will be given a copy of the signed form, either by email or printed on site directly following consent. Back up paper copies of all consent forms will be on hand in case of any power outages or Wi-Fi connectivity issues. Due to the child participants' age, informed consent will be obtained from the mother of the future child participant.

10.1.1.2 CONSENT PROCEDURES AND DOCUMENTATION

Documentation of Consent – The ICH GCP guidelines require that the participant or legal representative receive a copy of the signed and dated consent document. In this study the study participants will be asked to sign and date the informed consent document electronically and will be provided with a signed and dated copy by email or a printed copy. The source documents will thus reside in REDCapTM and will indicate that the consent was signed, along with the date of signing.

Translation of Consent Documents – All participants need to be able to speak and read English or Spanish. Therefore, all materials, including consents, will be translated and made available in English and Spanish.

10.1.2 STUDY DISCONTINUATION AND CLOSURE

This study may be prematurely terminated if there is sufficient reasonable cause. Written notification, documenting the reason for study suspension or termination, will be provided by the suspending or terminating party. If the study is prematurely terminated, the PI will promptly inform study participants, the IRB and NIDCR, and will provide the reason(s) for suspension or termination.

Circumstances that may warrant termination or suspension include, but are not limited to:

- Determination of unexpected, significant, or unacceptable risk to participants.
- Demonstration of efficacy that would warrant stopping.
- Insufficient compliance of study staff to the protocol (i.e., significant protocol violations).
- Data that are not sufficiently complete and/or evaluable.
- Determination that the primary endpoint has been met.
- Determination of futility.

10.1.3 CONFIDENTIALITY AND PRIVACY

Our research team will maintain rigorous protocols to ensure that data remain confidential. These methods include training of all research team members on issues of confidentiality and ethical research conduct, breaking the links between contact information and individual identifiers in the participant data, the use of secure passwords for access to data, and the use of secure filing cabinets. All researchers and staff will be required to keep all information collected by this project confidential. A REDCap[™] program at the UI will maintain the list linking each participant with a unique identifier. This list will be maintained in a physically separate location from the research database(s) with the unique identifier. The PI will have ultimate responsibility for managing and maintaining the data.

Participant confidentiality and privacy is strictly held in trust by the participating investigators, their staff, the safety and oversight monitor(s) and funding agency. This confidentiality is extended to the data being collected as part of this study. Data that could be used to identify a specific study participant will be held in strict confidence within the research team. No personally-identifiable information from the study will be released to any unauthorized third party without prior written approval of the sponsor/funding agency.

All research activities will be conducted in as private a setting as possible.

A study monitor, other authorized representatives of the IRB, may inspect all documents and records required to be maintained by the investigator, including but not limited to, records for the participants in this study.

The study participant's contact information will be securely stored for internal use only during the study. At the end of the study, all records will continue to be kept in a secure location for as

long a period as dictated by the reviewing UI IRB, Institutional policies, or sponsor/funding agency requirements.

Study participant research data, which is for purposes of statistical analysis and scientific reporting, will be transmitted to and stored at the Institute for Clinical and Translational Services (ICTS) at the UI using REDCapTM. This will not include the participant's contact or identifying information. Rather, individual participants and their research data will be identified by a unique study identification number. The study data entry and study data management system used by our research team will be secured and password protected. At the end of the study, all study databases will be de-identified and archived at ICTS.

10.1.4 FUTURE USE OF STORED SPECIMENS AND DATA

Stored specimens will be used for future studies. The participating child's samples will be stored with a code which may be linked to the child's name. If the mother agrees during the informed consent for future use of her child's samples but decide in the future that she would like to have it removed from future research, she should contact the PI. However, if some research with the child's samples had already been completed, the information from that research may still be used.

All paper-based data at the UI will be stored in the PI's locked private office within locked filing cabinets, including external hard drives with back up study data. Electronic data will be stored on the password-protected web-based REDCapTM site. No study data will remain on laptops after data collection visits end. All specimen and data will be stored for a minimum of six years upon study completion as dictated by the UI IRB.

Subjects may refuse or withdraw consent for collected samples and data to be used for future studies as described in the consent form. IRB will review future studies, and protections of confidentiality for any future studies with the stored specimens and/or data.

Role	Responsibilities
Principal Investigator [name], MS, PhD Professor and Chair Infant Oral Health Program Director Department of Pediatric Dentistry University of Iowa College of Dentistry [name] Office [contact] Office [contact] [contact]	 Study leadership Study design General study issues Protocol questions Reporting adverse events Data analysis Results interpretation Dissemination of findings Gold standard for calibration trainings Write abstracts, presentations Prepare manuscripts for publication
Program Official [name]	 Normal stewardship of the award Provide scientific, programmatic, and technical aspects of this project

